8.3 RECORDS

Electronic CRFs for individual patients will be provided by [REDACTED]

8.3.1 Source documents

In accordance with regulatory requirements, the Investigator should prepare and maintain adequate and accurate source documents and trial records that include all observations and other data pertinent to the investigation on each trial patient. Source data as well as reported data should follow good documentation practices and be attributable, legible, contemporaneous, original and accurate. Changes to the data should be traceable (audit trail).

Data reported on the CRF must be consistent with the source data or the discrepancies must be explained.

The current medical history of the patient may not be sufficient to confirm eligibility for the trial and the Investigator may need to request previous medical histories and evidence of any diagnostic tests. In this case the Investigator must make three documented attempts to retrieve previous medical records. If this fails, a verbal history from the patient, documented in their medical records, will be acceptable.

Before providing any copy of patients' source documents to the Sponsor, the Investigator must ensure that all patient identifiers (e.g., patient's name, initials, address, phone number, social security number) have properly been removed or redacted from any copy of the patients' source documents before sending them to the Sponsor.

Copies of tumour assessments scans may be collected by the Sponsor upon request. This could include CT scans of the chest and abdomen and/or imaging of any other known or suspected sites of disease (e.g., pelvis, brain) using an appropriate method (CT scan or MRI).

If the patient is not compliant with the protocol, any corrective action (e.g., re-training) must be documented in the patient file.

For the eCRF, data must be derived from source documents, for example:

- Patient identification: gender, year of birth (in accordance with local laws and regulations)
- Patient participation in the trial (substance, trial number, patient number, date patient was informed)
- Dates of patient's visits, including dispensing of trial medication
- Medical history (including trial indication and concomitant diseases, if applicable)
- Medication history
- Adverse events and outcome events (onset date [mandatory], and end date [if available])
- Serious adverse events (onset date [mandatory], and end date [if available])
- Concomitant therapy (start date, changes)
- Originals or copies of laboratory results and other imaging or testing results, with proper documented medical evaluation (in validated electronic format, if available)
- Completion of patient's participation in the trial (end date; in case of premature discontinuation document the reason for it).
- Prior to allocation of a patient to a treatment into a clinical trial, there must be documented evidence in the source data (e.g., medical records) that the trial participant

meets all inclusion criteria and does not meet any exclusion criteria. The absence of records (either medical records, verbal documented feedback of the patient or testing conducted specific for a protocol) to support inclusion/exclusion criteria does not make the patient eligible for the clinical trial.

- Technical information collected on PK sampling days (e.g., PK sampling times, repeated vital signs linked with PK) may be collected on specific paper PK logs, which will be considered as source data for related entries in the eCRF and are considered part of the ISF.

8.3.2 Direct access to source data and documents

[REDACTED] will monitor the conduct of the trial by regular on-site monitoring visits and in-house data quality reviews. The frequency of on-site monitoring will be determined by assessing all characteristics of the trial, including its nature, objective, methodology and the degree of any deviations of the intervention from normal clinical practice.

The Investigator /institution will allow site trial-related monitoring, audits, IRB review and regulatory inspections. Direct access must be provided to the eCRF and all source documents/data, including progress notes, copies of laboratory and medical test results, which must be available at all times for review by the monitor, auditor, and regulatory inspector (e.g., FDA). The monitor and auditor may review all eCRFs and informed consents. The accuracy of the data will be verified by direct comparison with the source documents described in Section 8.3.1. The Sponsor will also monitor compliance with the protocol and ICH GCP.

8.3.3 Storage period of records

Trial sites: The trial sites must retain the source and essential documents (including the ISF) according to contract or the local requirements valid at the time of the end of the trial (whatever is longer).

Sponsor: The Sponsor must retain the essential documents according to the Sponsor's SOPs.

[REDACTED] will retain trial documents according to contractual agreements with the Sponsor.

8.4 EXPEDITED REPORTING OF ADVERSE EVENTS

BI is responsible to fulfil their legal and regulatory reporting obligation in accordance with regulatory requirements. Exemptions from expedited reporting are described in Section 5.2.6.9, if applicable.

8.5 STATEMENT OF CONFIDENTIALITY AND PATIENT PRIVACY

Individual patient data obtained as a result of this trial is considered confidential and disclosure to third parties is prohibited with the exceptions noted below. Patient privacy will be ensured by using patient identification code numbers.

Data protection and data security measures are implemented for the collection, storage and processing of patient data in accordance with the principles 6 and 12 of the WHO GCP handbook.

Treatment data may be given to the patient's personal physician or to other appropriate medical personnel responsible for the patient's welfare. Data generated as a result of the trial need to be available for inspection on request by the participating physicians, the Sponsor's representatives, by the IRB/IEC and the regulatory authorities.

8.6 TRIAL MILESTONES

The **start of the trial** is defined as the date when the first patient in the whole trial signs informed consent.

The **end of the trial** is defined as the date of the last visit (including all follow-up visits) of the last patient in the whole trial ("Last Subject Completed" = 6 months after the last patient completed the 30-day safety follow-up visit in Parts A and B, and 12 months after the last patient completed the 30-day safety follow-up in Part C).

The "**Last Subject Last Treatment**" date is defined as the date on which the last patient at an individual trial site ends trial medication (as scheduled per protocol or prematurely). Individual Investigators will be notified of SUSARs occurring with the trial medication until 30 days after this date at their site.

The "**Last Patient Last Visit Primary Endpoint (LPLV PE)**" is defined as the date at which the last patient was examined or received an intervention for the purposes of final collection of data for the primary endpoint (according to the protocol specified schedule or after premature discontinuation) for each part of the trial. Patient treatment and follow up may continue after this time point. For Parts A and B, this is the last visit in the first cycle of the last patient in the respective part. A CSR will be considered at these time points. For Part C, this is the date when the last subject was treated for at least 18 weeks. At this time, the CSR will report the analysis of all primary and secondary endpoints. The CSR will be revised after "last subject completed".

Early termination of the trial is defined as the premature termination of the trial due to any reason before the end of the trial as specified in this protocol.

Temporary halt of the trial is defined as any unplanned interruption of the trial by the Sponsor with the intention to resume it.

Suspension of the trial is defined as an interruption of the trial based on a Health Authority request.

The IEC / competent authority in each participating EU member state will be notified about the trial milestones according to the respective laws.

A final report of the clinical trial data will be written only after all patients have completed the trial in all countries (EU or non-EU) to incorporate and consider all data in the report. The Sponsor will submit to the EU database a summary of the final trial results within one year from the end of a clinical trial as a whole, regardless of the country of the last patient (EU or non-EU).

8.7 ADMINISTRATIVE STRUCTURE OF THE TRIAL

The trial is sponsored by Boehringer Ingelheim (BI).

A contract research organisation, [REDACTED], is responsible for project management, medical management, site management, data management, site regulatory document management, management of the Trial Master File, some aspects of safety management and reporting, medical writing, and medical monitoring.

A Safety Review Committee (SRC) will be established. Members of the SRC will include:

- [REDACTED] Medical Monitor for the trial, or delegate
- Principal Investigators, or delegates, from each investigational site
- BI Safety Physician, or delegate
- BI Clinical Program Leader, or delegate, responsible for the project.

The BI Safety Physician (or delegate), BI Clinical Program Leader (or delegate) should always attend the SRC to discuss safety issues.

[REDACTED] Medical Monitor, or delegate, should always be present at the SRC. Other BI and non-BI subject matter experts may also be invited, as appropriate. The SRC documentation for this trial will define the exact membership and who should be present for decisions to be made.

The SRC will be responsible for assessing the progress of the clinical trial, including making safety and efficacy assessments at specified intervals, making dose-escalation decisions for BI 891065, making dose selection decisions for BI 754091, making decisions on the next cohort size, and recommending to the Sponsor whether to continue, modify, or stop the trial. To support their decision making, the SRC will have unblinded access to data from this trial and the ongoing studies, BI 1381.1 and BI 1381.2, which evaluate BI 754091. Minutes from these meetings will be prepared and circulated to the trial team and each investigator for comment prior to finalisation.

The tasks and responsibilities of the SRC will be documented. The SRC will maintain written records of all its meetings.

Relevant documentation on the participating investigators and other important participants, including their curricula vitae, will be filed in an Investigator Site File (ISF).

The statistical analysis will be done by BI according to BI Standard Operating Procedures (SOPs).

Tasks and functions assigned in order to organise, manage, and evaluate the trial are defined according to BI SOPs and [REDACTED] SOPs as agreed upon and documented. A list of responsible persons and relevant local information can be found in the ISF.

An Interactive Response Technology (IRT) vendor will be used in this trial for development of shipment orders and assignment of trial medication.

[REDACTED] Study Chair is responsible for coordinating investigators at the different sites participating in this trial. Tasks and responsibilities are defined in a contract.

BI has appointed a Trial Clinical Monitor, responsible for coordinating all required activities, in order to

- manage the trial in accordance with applicable regulations and internal SOPs,
- direct the clinical trial team in the preparation, conduct, and reporting of the trial.

The organisation of the trial in the participating countries will be performed by [REDACTED] [REDACTED] with which the responsibilities and tasks will have been agreed and a written contract filed before initiation of the clinical trial.

A central laboratory service will be used in this trial. Details will be provided in the Central Laboratory Manual, available in the ISF.

10. APPENDICES

10.1 IMMUNE-RELATED ADVERSE EVENTS OF SPECIAL INTEREST

Table 10.1: 1 Immune-related adverse events of special interest*

Immune-related adverse events of special interest
Pneumonitis (reported as an irAE if \geq Grade 2)

 • Acute interstitial pneumonitis • Interstitial lung disease • Pneumonitis
Colitis (reported as an irAE if \geq Grade 2 or any grade resulting in dose modification or use of systemic steroids to treat the AE)

 • Intestinal obstruction • Colitis • Colitis microscopic • Enterocolitis • Enterocolitis haemorrhagic • Gastrointestinal perforation • Necrotizing colitis • Diarrhea
Endocrine (reported as an irAE if \geq Grade 3 or \geq Grade 2 and resulting in dose modification or use of systemic steroids to treat the AE)

 • Adrenal insufficiency • Hyperthyroidism • Hypophysitis • Hypopituitarism • Hypothyroidism • Thyroid disorder • Thyroiditis • Hyperglycaemia, if \geq Grade 3 and associated with ketosis or metabolic acidosis
Endocrine (reported as an irAE)

 • Type 1 diabetes mellitus (if new onset)

Table 10.1: 1 Immune-related adverse events of special interest (continued)

Hematologic (reported as an irAE if \geq Grade 3 or any grade resulting in dose modification or use of systemic steroids to treat the AE)
 
 • Autoimmune haemolytic anaemia • Aplastic anaemia • Thrombotic thrombocytopenic purpura • Idiopathic (or immune) thrombocytopenia purpura • Disseminated intravascular coagulation • Haemolytic-uraemic syndrome • Any Grade 4 anaemia regardless of underlying mechanism

Hepatic (reported as an irAE if \geq Grade 2, or any grade resulting in dose modification or use of systemic steroids to treat the AE)
 
 • Hepatitis • Autoimmune hepatitis • Transaminase elevations (ALT and/or AST)

Infusion Reactions (reported as an irAE for any grade)
 
 • Allergic reaction • Anaphylaxis • Cytokine release syndrome • Serum sickness • Infusion reactions • Infusion-like reactions

Neurologic (reported as an irAE for any grade)
 
 • Autoimmune neuropathy • Guillain-Barre syndrome • Demyelinating polyneuropathy • Myasthenic syndrome

Ocular (report as an irAE if \geq Grade 2 or any grade resulting in dose modification or use of systemic steroids to treat the AE)
 
 • Uveitis • Iritis

Table 10.1: 1 Immune-related adverse events of special interest (continued)

Renal (reported as an irAE if ≥ Grade 2)

 • Nephritis • Nephritis autoimmune • Renal failure • Renal failure acute • Creatinine elevations (report as an irAE if ≥Grade 3 or any grade resulting in dose modification or use of systemic steroids to treat the AE)
Skin (reported as an irAE for any grade)

 • Dermatitis exfoliative • Erythema multiforme • Stevens-Johnson syndrome • Toxic epidermal necrolysis
Skin (reported as an irAE if ≥ Grade 3)

 • Pruritus • Rash • Rash generalized • Rash maculopapular • Any rash considered clinically significant in the physician's judgment
Other (reported as an irAE for any grade)

 • Myocarditis • Pancreatitis • Pericarditis • Any other Grade 3 event that is considered immune-related by the physician

*Immune-related AEs should be reported as AESIs only for patients who received immunotherapy.

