5.2.6.4.2 BI 754091 infusion-related reactions

Infusion-related reactions CTCAE Version 5.0 Grade ≥ 2 are defined as AESIs.

The following terms describe those events that are to be considered potential infusion-related AEs. These events are considered as AESIs and must be reported to the [REDACTED]

[REDACTED] Safety group within 24 hours of the event:

- Allergic reaction
- Anaphylaxis
- CRS
- Serum sickness
- Infusion reactions
- Infusion-like reactions

If the Investigator determines that another event (not on the list) may be a potential infusion-related AE, the Investigator may also report that event as an AESI.

In the event of an infusion-related reaction \leq Grade 2, the infusion rate of BI 754091 may be decreased by 50% or interrupted until resolution of the event and re-initiated at 50% of the

initial rate until completion of the infusion. In patients experiencing infusion-related reactions \leq Grade 2, subsequent infusions may be administered at 50% of the initial rate.

If a patient experiences an infusion-related reaction, acetaminophen and/or an antihistamine (e.g., diphenhydramine) and/or corticosteroid or equivalent medication per institutional standard may be administered prior to subsequent infusions at the discretion of the Investigator for secondary prophylaxis of infusion-related reactions. If an infusion-related reaction is Grade 3 or higher in severity at any point during the trial, treatment with BI 754091 will be permanently discontinued.

As with any mAb, allergic reactions to dose administration are possible. Appropriate drugs and medical equipment to treat acute anaphylactic reactions must be immediately available, and trial personnel must be trained to recognise and treat anaphylaxis. All trial sites will have emergency resuscitation services and access to intensive care available.

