5.2.6.4.3 Cytokine release syndrome

Events of CRS CTCAE Version 5.0 Grade ≥ 2 are defined as AESIs. Patients will be closely monitored for CRS and, in case of suspected or confirmed CRS, appropriate treated according to best medical judgement based on institutional standards and/or publications (e.g., Lee et al. 2016 [R16-2323]). For the treatment of CRS, supportive therapy including steroids and / or interleukin 6 receptor (IL6R) antagonists (R15-0031) may be used as clinically indicated.

For Part A:

- Patients will remain under surveillance for 10 hours after first administration of BI 891065 [REDACTED]
- Patients will remain under surveillance for at least 8 hours after the second and third administrations of BI 891065.

For Part B:

- Patients will remain under surveillance after the administration of BI 891065 [REDACTED] in combination with BI 754091 [REDACTED] during Cycles 1 and 2.
- Duration of surveillance will be for 8 hours after the first dose of BI 891065 during Cycle 1, and for 6 hours after the first dose of BI 891065 in Cycle 2

For Part C:

- Patients will remain under surveillance after the administration of BI 891065 [REDACTED] in combination with BI 754091 [REDACTED] during Cycles 1 and 2.
- Duration of surveillance will be for 4 hours after the first dose of BI 891065 during Cycles 1 and 2.

Although patients will not be required to stay overnight on the first day of monotherapy or combination therapy treatments, they should be advised to remain close to the study site where medical coverage will be ready to support them, if required. Thereafter, patients will

be monitored with regular safety visits. All trial sites will have emergency resuscitation services and access to intensive care available.

Monitoring will include measurement of body temperature, heart rate, and blood pressure at regular intervals as presented in [Part A Flow Chart](#), [Part B Flow Chart](#), and [Part C Lung Flow Chart](#). Patients will be assessed for signs or symptoms of CRS (e.g., hypotension, hypoxia, tachycardia, fever, nausea, fatigue, headache, myalgias, and malaise).

Patients will be informed about possible signs and symptoms of CRS, and the need to immediately contact or present to the investigational site if symptoms occur after discharge.

The following recommendations for the management of CRS regarding administration of BI 754091 and BI 891065 should be considered by the Investigator as guidance:

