5.2.6.4.4 Immune-related adverse events (irAE)

Immune-related AEs are AEs associated with immunotherapy treatments that appear to be associated with the immune therapy's mechanism of action. These adverse reactions, which can be severe, may involve the gastrointestinal, skin, liver, endocrine, respiratory, renal, or other organ systems. The Sponsor has defined a list of potential irAEs in [Table 10.1: 1](#) in [Appendix 10.1](#). These irAEs must be reported as AESIs. If an Investigator determines another event (not on the list) should be a potential irAE, the Investigator may also report that event as an AESI. Immune-related AEs should be reported as AESIs only for patients who received immunotherapy.

Recommendations for the management of irAEs are presented in [Appendix 10.2](#).

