7.8.1 Adverse events

The analyses of AEs will be descriptive in nature. All analyses will be based on the number of patients with AEs (not on the number of AEs). The analysis will be based on BI standards (6). AEs will be coded using the most recent version of MedDRA. According to the BI standards multiple overlapping or adjacent recordings (AE occurrences) of the same AE are collapsed into one AE event if all AE attributes are identical (lower level term, severity, action taken, therapy required, seriousness, reason for seriousness, relationship, outcome, AE of special interest (AESI) flag).

The analyses of AEs will be based on the concept of treatment-emergent AEs, where a treatment-emergent AE has an onset in the analysing treatment period. The AE analysis will be based on the on-treatment period which starts with the date of the first administration of study medication and ends 30 days after the last administration of study medication. AEs with an onset date in the screening period (time between informed consent date and date of the first administration of study medication) or follow-up period (time after the on-treatment period) will be tabulated and listed separately.

Sorting order: In AE tables, system organ classes (SOCs) will be sorted alphabetically and preferred terms (PTs, within SOCs) will be sorted by descending frequency.

Listings of AEs will be displayed by patient. The actual planned dose of BI 891065/dose combination of BI 891065 and BI 754091 will be derived and included in the listings. AEs will be reported with start day and end day as calculated from the first day of treatment with study medication. For listings displaying AEs during the screening or follow-up period, the start and stop day are calculated from the start of the respective analysis period.

The incidence of AEs overall, related AEs, serious AEs (SAEs), and immune-related AEs will be reported by severity according to common terminology criteria for adverse events (CTCAE) grades (CTCAE version 4.03 for Part A, CTCAE version 5.0 for Part B and Part C). Drug-related serious AEs will also be tabulated. Protocol-specified AESI will be analysed based on data reported in the eCRF.

AEs leading to death during the on-treatment period will be tabulated by SOC and PT. Reported fatal AEs during the follow-up period will be listed.

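### For patients given BI 754091, the protocol sets two AESI thresholds for infusion reactions and cytokine release syndrome (Grade ≥ 2 and any grade), and SAP 7.8.1 states no grade rule to settle which one the AESI display uses

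*Protocol*

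**What the plan says.** Four places in the protocol bear on whether an infusion reaction or CRS is an AESI.

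- Section 5.2.6.4.2 opens with a graded rule: "Infusion-related reactions CTCAE Version 5.0 Grade ≥ 2 are defined as AESIs". It then lists six terms (allergic reaction, anaphylaxis, CRS, serum sickness, infusion reactions, infusion-like reactions) with no grade and says of them: "These events are considered as AESIs and must be reported to the" safety group within 24 hours.
- Section 5.2.6.4.3 gives the graded rule for CRS: "Events of CRS CTCAE Version 5.0 Grade ≥ 2 are defined as AESIs".
- Section 5.2.6.4.4 refers to the list in Table 10.1: 1 and says: "These irAEs must be reported as AESIs". That table has a row headed "Infusion Reactions (reported as an irAE for any grade", which contains the same six terms as Section 5.2.6.4.2. Section 5.2.6.4.4 and the table footnote limit this route to patients who received immunotherapy.
- Section 1.4 also calls infusion-related reactions and CRS AESIs without a grade. It is a summary that points to the detailed sections.

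Section 5.2.6.4 gives AESIs the same reporting time frame as serious adverse events, which Section 5.2.6.7.2 sets at 24 hours.

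On the analysis side, SAP 7.8.1 says: "Protocol-specified AESI will be analysed based on data reported in the eCRF". The same section counts an AESI flag among the recorded attributes of an adverse event. The visible SAP text gives no grade rule for AESIs.

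**The concern.** A site that relies on the opening sentence of Section 5.2.6.4.2, or on Section 5.2.6.4.3, will not flag a Grade 1 infusion reaction or Grade 1 CRS as an AESI. A site that relies on the ungraded term list in Section 5.2.6.4.2, or on Table 10.1: 1, will flag it and report it within 24 hours. Both can say that they followed the protocol.

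If the AESI display is built from the flag, its count for these terms can differ between cohorts because different sites enrolled the patients, and not only because of dose. Within that display a reader could not tell an absence of Grade 1 events from an absence of flags. On the conduct side, sites lack a clear instruction on whether a Grade 1 event starts the 24-hour clock.

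**Working it through.** The point rests on no sample size, power or event-rate figure, so there is no plan figure to reproduce. The check is a comparison of the rules.

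**Step 1. Apply each rule to the same event in a patient given BI 754091.**

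| Protocol text | Grade 1 infusion reaction | Grade 1 CRS | Grade ≥ 2, either |
|---|---|---|---|
| 5.2.6.4.2, graded sentence | not covered | – | AESI |
| 5.2.6.4.2, ungraded list | AESI | AESI | AESI |
| 5.2.6.4.3, graded sentence | – | not covered | AESI |
| 5.2.6.4.4 with Table 10.1: 1 | AESI | AESI | AESI |
| 1.4, summary statement | AESI | AESI | AESI |

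The rules agree from Grade 2 upwards and differ only at Grade 1. Section 5.2.6.4.2 is not consistent even within itself.

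**Step 2. Is the any-grade wording in the table deliberate?** Other rows of Table 10.1: 1 carry their own thresholds. Pneumonitis is listed from Grade 2. Haematologic events are listed from Grade 3, or at any grade with dose modification or systemic steroids. The any-grade entry for infusion reactions is thus a specific threshold and cannot be dismissed as a loose label.

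**Step 3. Who is affected?** The table route applies only to patients who received immunotherapy. If that means BI 754091, Part A monotherapy patients fall under the graded CRS rule of Section 5.2.6.4.3. SAP Section 4 states that Part C was cancelled with no patients. That leaves Part B.

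**Step 4. Which outputs are affected?**

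- Protocol 5.2.6.7.1 collects all adverse events from consent to the end of the residual effect period, and 5.2.6.5 has severity recorded by CTCAE grade. SAP 7.8.1 reports adverse events by CTCAE grade, and SAP 6.1 and 7 present them by dose cohort. Those tables do not depend on the AESI flag.
- A Grade 1 infusion reaction or Grade 1 CRS meets none of the DLT criteria in Protocol 4.1.8. It does not enter the dose-escalation model or the MTD.
- The AESI display does depend on it, to the extent that it uses the flag.

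**Step 5. How sensitive is that display?** The documents give no Grade 1 rate, so the number of patients cannot be derived. The effect of one patient being flagged differently can be. Protocol Table 7.1.2: 5 shows Part B cohorts of 5, 6 and 8 evaluable patients:

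- 1/5 = 20.0 percentage points
- 1/6 = 16.7 percentage points
- 1/8 = 12.5 percentage points

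These are illustrations. The AESI analysis uses the treated set, which may be somewhat larger than the evaluable set.

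**The case against.** The strongest reply is that the provisions are cumulative. Section 5.2.6.4 lists several separate routes to AESI status, and meeting one is enough. The two graded sentences say that Grade ≥ 2 events are AESIs; they do not say that Grade 1 events are not. On that reading a Grade 1 event in a patient given immunotherapy is an AESI through the table, and the graded CRS rule still has work to do in Part A.

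Part of this stands. A reader might infer a flat contradiction, in which a Grade 1 event both is and is not an AESI. The text does not go that far, because the cumulative reading is available. But under that reading the graded sentence on BI 754091 infusion reactions has no function: the ungraded list directly below it and the table already cover every grade. A site could reasonably assume that the sentence was meant to limit something, so both practices remain defensible.

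A second reply is that eCRF data include term and grade as well as the flag, and that the sponsor's adverse event standard or the SAP technical documents may settle the derivation. Those documents cannot be seen here. This is why the claim is that the display can reflect flagging practice, not that it will. Divergent behaviour between sites is possible and is not shown.

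A third reply is that Grade 1 infusion reactions and CRS will appear by dose in the general adverse event tables whatever was flagged. That is correct and limits the point to the AESI display and to expedited reporting.

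**Conclusion.** The point holds in a narrow form and is minor. For patients given BI 754091 the protocol offers two AESI thresholds for infusion reactions and CRS, and the visible SAP does not say which one the AESI analysis applies. Flagging and 24-hour reporting of Grade 1 events, and possibly the AESI display, can therefore vary with the section a site followed. This assumes that receiving immunotherapy means receiving BI 754091, and that no unseen standard fixes the grade rule.

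Three stronger inferences are tempting and are not supported.

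- **That a main safety result is compromised, or that dose levels cannot be compared.** The primary endpoints of Parts A and B are the MTD and first-cycle DLTs. The synopsis names adverse event incidence and severity and QTcF as the safety criteria. AESI analysis gets one sentence in SAP 7.8.1, and comparison by dose remains possible from the graded adverse event tables.
- **That a known number of patients moves in or out of the table.** Assuming a Grade 1 rate of 10% to 20% in the planned 31 to 37 Part B patients gives 0.10 × 31 = 3.1 to 0.20 × 37 = 7.4, about 3 to 7. At 5% the lower figure is 0.05 × 31 = 1.55, about 2, and a rate near zero cannot be excluded. The rate is assumed throughout, and the count matters only if sites applied different rules.
- **That DLT or MTD results are touched.** They are not.

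**What to change.** In the protocol, reconcile Sections 5.2.6.4.2 (both the graded sentence and the ungraded list), 5.2.6.4.3 and 5.2.6.4.4 and Table 10.1: 1 to one AESI threshold for infusion reactions and CRS, and align the summary statement in Section 1.4. State whether the threshold differs between monotherapy and combination patients. The choice of threshold belongs to the sponsor.

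In SAP 7.8.1, derive the AESI counts for infusion reactions and CRS from preferred term and recorded CTCAE grade, and show them for any grade and for Grade ≥ 2, so that they no longer rest on the site's AESI flag alone. Both variables are already collected, so this works for data already in the database and whichever threshold is chosen. It does not change which Grade 1 events were or were not sent within 24 hours.

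The cost is protocol wording and one extra table derivation. Classification: wrong as written, minor.
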